### Lateralization.

Subjects will have skin electrodes affixed to locations around their body (wrist, forearm, and base of the neck) and head (mastoids, forehead and nape of the neck) and will be placed in an acoustically sealed test room at Mayo Clinic. Two or more pairs of electrodes will be chosen until all 12 possible combinations are tested for current level and timing. At each test point, the perception threshold will be evaluated by increasing the amplitude of the current input until the subject can hear a tone. The threshold will be recorded as the perception threshold at that electrode pair and frequency.

Once the threshold is determined, the user will be asked to identify where they hear the sound and recorded on a 3-dimensional spherical plot. This angle will be recorded as the lateralization point at that electrode pair and frequency.

### Modified Rhyme Test

The MRT is a speech intelligibility test consisting of a set of 50 six-item wordlists. Each word list contains single syllable words with a consonant-vowel-consonant sound sequence. Each group of words either rhymes (e.g., led, shed, red, bed, fed, wed) or starts with the same sound (e.g., sud, sum, sub, sun, sup, sung). The MRT is one of the speech intelligibility tests referred to in the American National Standard Method for Measuring the Intelligibility of Speech Over Communication Systems and is often used to test military communication systems.

### First phase clinical trial:

1) 30 normal hearing participants will be recruited to measure amplitude, threshold, lateralization, and speech intelligibility using the prototype compared to conventional acoustic measures.

2) Parameters for electrode interaction between two channels of electrical stimulation by level of current and timing will be measured in the same participant pool.

3) Algorithms will be established for surround sound based upon the electrode interaction data.

Subjects will be seated in a comfortable chair in a sound treated test room (100dB of attenuation from outside sound). Standard insert earphones and surface electrodes will be used in acoustic and electrostimulation respectively. Acoustic signals will be generated by a standard diagnostic audiometer used in hearing evaluations. Electroacoustic signals will be generated by the Vivonics programmable prototype. The participant will respond to the auditory signals to indicate the lowest level of perception, the location of the signal within the head, and word recognition using a standard work recognition test.

Second phase clinical trial:

1) 15 bilateral hearing impaired, and 15 asymmetrical hearing-impaired participants will be recruited to evaluate directionality of the surround sound system for speech and music,

2) 30 normal hearing participants will be recruited to implement amplitude adjustments to offset simulated cochlear hearing loss with narrowband masking noise and compare the findings to standard acoustic measures of threshold and speech recognition.

Subjects will be seated in a comfortable chair in a sound treated test room (100dB of attenuation from outside sound). Standard insert earphones, bone conduction, and surface electrodes will be used in acoustic and electrostimulation respectively. Acoustic signals will be generated by a standard diagnostic audiometer and bone conduction used in hearing evaluations. Electroacoustic signals will be generated by the Vivonics programmable prototype. The participant will respond to the auditory signals to indicate the lowest level of perception, the location of the signal within the head, and word recognition using a standard work recognition test.

Standard clinical narrowband masking noise will be used to simulate hearing loss and assess the suprathreshold perception of electric signals. Narrowband masking noise will be introduced via earphones and will be presented at suprathreshold levels between 25-50 dB HL at all frequencies. The masking noise of a maximum of up to 50 dB HL is below than the sound levels categorized as “loud sound (> 85 dB SPL). In fact, the sound levels of normal speech are around 60 dB SPL. While this is occurring, the skin electrodes will be used as reported above, and the perception of the threshold will be evaluated with the addition of masking noise. This is to simulate a higher hearing threshold and assess if the electric signal can still be heard over the masking noise. This protocol is to further develop the modeling from the first phase that will be used to predict electric thresholds using air conduction threshold inputs.

In the second phase 8-space will be utilized which is an 8-speaker system that provide independent sound source as an evaluation of localization. The localization experiment will include electrostimulation data from the first phase in combination with a prototype multi-microphone headset to evaluate the necessary parameters for precise localization for bilateral, unilateral, and normal hearing participants. A signal-to-noise ratio of various levels will be adjusted to evaluate the efficacy of the noise cancellation system developed by MCK Audio. Participants will be asked to rate the quality of music of the electroacoustic system on a 1-10 scale.

**Third phase clinical trial:**

- 1) 30 normal hearing participants will be recruited to evaluate parameters of electrical stimulation for body-worn electrodes. Laterality and amplitude measures will be assessed for tone and speech stimuli.
- 2) All of the methods used in Phase 3 have been previously described and approved for Phases 1 and 2, with the difference lying in where the electrodes are placed on the body for Phase 3.

Following informed consent, the investigators will evaluate the auditory perception and magnitude of electrical stimulation at the wrist, forearm, and base of the neck by comparing the responses to those established at the forehead, mastoids, and neck. Each threshold from 250Hz through 20 KHz will be determined with a method of limits approach for both acoustic and electrostimulation. Once these thresholds are established, then we will test speech recognition at these distal locations by measuring percent correct in MRT testing at a suprathreshold level.

Of primary interest is the assessment of lateralization of sound when the electrodes are placed on the wrist, forearm, and back by employing unique channels of electrostimulation to determine the place and degree of separation of sound compared to the traditional lateralization of ear-to-ear with traditional acoustic hearing. Participants will have electrodes affixed to the three locations on their body (wrist, forearm, and base of the neck), and a matrix of possible combinations will be tested for perception threshold and location. At each test point, the perception threshold will be evaluated by increasing the amplitude of the current input until the subject can hear a tone. The location of the sound will be recorded on the three-dimensional spherical plot.

**Subject Information**

*Target accrual is the proposed total number of subjects to be included in this study at Mayo Clinic. A "Subject" may include medical records, images, or specimens generated at Mayo Clinic and/or received from external sources.*

Target accrual: 100 subjects (30 for phase 1, 60 for phase 2, 30 for phase 3)

Subject population (children, adults, groups): Adults over the age of 21

Inclusion Criteria: Age range of 21-75

Exclusion Criteria: Pregnant, cochlear implants, history of fluctuating sensorineural hearing loss, skin diseases of the head, history of acute paroxysmal tachycardia, history of trigeminal neuralgia, recent or paralysis of the facial nerve, recent cerebrovascular stroke

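### The target accrual of 100 subjects does not match its own phase breakdown, which adds to 120, and no overlap between phases is stated

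*Protocol*

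**What the plan says.** Subject Information gives the total and its parts in one line: "Target accrual: 100 subjects (30 for phase 1, 60 for phase 2, 30 for phase 3". The form text just above defines target accrual as the total number of subjects proposed for the study at the site.

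Study Design and Methods describes who fills each phase:

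- Phase 1: "30 normal hearing participants will be recruited to measure amplitude, threshold, lateralization, and speech intelligibility". A second item says that the electrode-interaction parameters "will be measured in the same participant pool", that is, in the Phase 1 group.
- Phase 2, hearing impaired: "15 bilateral hearing impaired, and 15 asymmetrical hearing-impaired participants will be recruited to evaluate directionality".
- Phase 2, normal hearing: "30 normal hearing participants will be recruited to implement amplitude adjustments to offset simulated cochlear hearing loss".
- Phase 3: "30 normal hearing participants will be recruited to evaluate parameters of electrical stimulation for body-worn electrodes".

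Key Objectives lists a characterization study of 30, then a noise-cancellation trial of 20 normal-hearing, 20 bilateral sensorineural and 20 single-sided-deafness participants. It does not mention the third phase.

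**The concern.** A total and its breakdown stand in the same line and disagree. A reader cannot tell whether 120 separate people are planned, or 100 people of whom some take part more than once.

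The two plans differ in more than headcount, because the phases draw on each other. Phase 3 evaluates the wrist, forearm and base of the neck "by comparing the responses to those established at the forehead, mastoids, and neck". The masking work in Phase 2 is meant to "further develop the modeling from the first phase that will be used to predict electric thresholds". If the phases enrol different people, such comparisons are between independent groups. If some people appear in two or three phases, part of the data is correlated within person, and treating it as independent would be wrong.

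**Working it through.** **Inputs.** Stated total: 100 (Subject Information). Phase sizes: 30, 60, 30 (same line). Components: Phase 1, 30 normal hearing; Phase 2, 15 bilateral, 15 asymmetrical and 30 normal hearing; Phase 3, 30 normal hearing (Study Design and Methods). The protocol gives no dropout rate, and its power statement is marked as not applicable.

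**Step 1: try to reproduce 100.**

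- From the line itself: 30 + 60 + 30 = 120.
- From the phase descriptions: 30 + (15 + 15 + 30) + 30 = 120.
- Phases 1 and 2 only: 30 + 60 = 90.
- Key Objectives: 30 + (20 + 20 + 20) = 90. Adding the 30 of Phase 3 from the methods gives 120.

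No straight sum gives 100. Dropout does not explain it either: 120 × (1 − d) = 100 needs d = 20/120 = 16.7%, no such rate is stated, and the bracket is presented as the breakdown of the 100.

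**Step 2: size of the gap.** 120 − 100 = 20 people, which is 20/100 = 20% of the stated total, or 20/120 = 16.7% of the sum.

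**Step 3: what 100 unique people would require.** Keep the phase sizes in Study Design and Methods.

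- Hearing-impaired people: 15 + 15 = 30. They appear in Phase 2 only and cannot fill normal-hearing places.
- Normal-hearing places: 30 + 30 + 30 = 90.
- Normal-hearing people available: 100 − 30 = 70.
- Let x be the number of people in exactly two phases and y the number in all three. Each of the x fills one extra place and each of the y fills two, so x + 2y = 90 − 70 = 20.
- The number of repeat participants, x + y, then runs from 10 (x = 0, y = 10) to 20 (x = 20, y = 0).

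**Step 4: is there a route to 100 in the text?** One can be built. Take the 20/20/20 split from Key Objectives for Phase 2 and draw its 20 normal-hearing participants from Phase 1: 30 + 20 + 20 + 30 = 100. But Study Design and Methods splits Phase 2 as 15/15/30, and neither section states such reuse.

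**Illustration only; no such analysis is planned.** Suppose 100 were a hard cap, the phases ran in sequence and nobody took part twice. Phase 3 would then have 100 − 90 = 10 people instead of 30. The 95% confidence-interval half-width for a mean is t(0.975, n − 1)/√n in SD units: 0.72 SD at n = 10 against 0.37 SD at n = 30. The protocol sets no such cap.

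**The case against.** The best counter-argument is that the sum is not wrong and the overlap is merely unstated. Target accrual counts people, the bracket counts places per phase, and normal-hearing adults fill 90 of the 120 places. Some text is compatible with reuse: the Phase 2 localization work includes electrostimulation data from the first phase, Phase 3 is compared with responses at the head sites, and the Lateralization section describes body and head electrodes on the same subjects. Saying that participants are to be recruited does not rule out re-enrolment.

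This stands in part: overlap is possible, and 120 is not proven to be the intended figure. It does not remove the contradiction. Every group in every phase is described as recruited, and the one place that reuses people, within Phase 1, says so explicitly. If overlap was intended, the protocol still has to state it.

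Three further objections limit the weight of the point. Key Objectives alone sums to 90, and reaches 120 only with Phase 3 borrowed from the methods, so it is not independent confirmation. The interval widths in the illustration rest on a cap that the document does not set. No formal between-phase test is stated, and how repeated participants would be modelled can be left to a statistical analysis plan. All three are fair. The finding rests only on the total, its breakdown and the phase descriptions.

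**Conclusion.** The concern holds. The stated total of 100 contradicts its own breakdown by 20 people, and the phase descriptions support each part of the breakdown. The line is complete, with no redaction or broken text to explain the gap.

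That 120 separate people are meant is the more natural reading, but it is an inference. If 100 unique people were meant, with the Phase 2 split in Study Design and Methods, between 10 and 20 normal-hearing people would have to take part more than once.

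The consequence is real but limited. This is the study's only total sample size, and the reading determines whether cross-phase data are independent. No power calculation or stopping rule depends on it, the phase sizes themselves are consistent, and no loss of precision follows from the discrepancy alone. It should be corrected, but it does not undermine the design.

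**What to change.** Make the total agree with its breakdown in Subject Information, in one of two ways.

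1. If the phases enrol separate people, restate the target accrual as 120 subjects: 30 for Phase 1, 60 for Phase 2 and 30 for Phase 3.
2. If 100 unique people were meant, keep 100 and say which groups may enter more than one phase and how many people do so. With the current phase sizes the numbers must satisfy (people in exactly two phases) + 2 × (people in all three) = 20. Any comparison between phases should then allow for repeated participants, for example through a mixed model with a random participant effect; that detail may sit in the analysis plan.

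The cost is one corrected number, or one or two sentences, in a protocol modification. The phase sizes already described do not change.

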**Biospecimens-NOT APPLICABLE TO THIS STUDY**

Collection of blood samples. When multiple groups are involved copy and paste the appropriate section below for example repeat section b when drawing blood from children and adults with cancer.

a. **From healthy, non-pregnant, adult subjects who weigh at least 110 pounds.** For a minimal risk application, the amount of blood drawn from these subjects may not exceed 550ml in an 8 week period and collection may not occur more frequently than 2 times per week.

Volume per blood draw: \_\_\_\_\_ ml

Frequency of blood draw (e.g. single draw, time(s) per week, per year, etc.) \_\_\_\_\_

b. **From other adults and children considering age, weight, and health of subject.** For a minimal risk application, the amount of blood drawn from these subjects may not exceed the lesser of 50 ml or 3 ml per kg in an 8 week period, and collection may not occur more frequently than 2 times per week.

Volume per blood draw: \_\_\_\_\_ ml

Frequency of blood draw (e.g. single draw, time(s) per week, per year, etc.) \_\_\_\_\_

Prospective collection of biological specimens other than blood: \_\_\_\_\_

#### Review of medical records, images, specimens

Check all that apply (data includes medical records, images, specimens).

Only data that exists before the IRB submission date will be collected.

#### Date Range for Specimens and/or Review of Medical Records:

Examples: 01/01/1999 through 12/31/2015, or all records through mm/dd/yyyy.

Note: The Date Range must include the period for collection of baseline data, as well as follow-up data, if applicable.

The study involves data that exist at the time of IRB submission **and** data that will be generated after IRB submission. Include this activity in the Methods section.

Examples

- The study plans to conduct a retrospective chart review and ask subjects to complete a questionnaire.
- The study plans to include subjects previously diagnosed with a specific disease and add newly diagnosed subjects in the future.

The study will use data that have been collected under another IRB protocol. Include in the Methods section and enter the IRB number from which the research material will be obtained. *When appropriate, note when subjects have provided consent for future use of their data and/or specimens as described in this protocol.*

Enter one IRB number per line, add more lines as needed

Data  Specimens  Data & Specimens \_\_\_\_\_

Data  Specimens  Data & Specimens \_\_\_\_\_

Data  Specimens  Data & Specimens \_\_\_\_\_

### Data Analysis

*Power analyses may not be appropriate if this is a feasibility or pilot study, but end-point analysis plans are always appropriate even if only exploratory. Provide all information requested below, or provide justification if not including all of the information.*

Power Statement: Not applicable at this time, technology currently in development

Data Analysis Plan: This

Data Analysis Plan: This systematic approach will provide the electrical hardware needs for prototype development, will characterize the electrode location dynamics, and will demonstrate the feasibility of clear speech understanding using the proposed concept. Furthermore, the resultant data can be extrapolated across other frequencies and input currents to deliver a highly effective and safe prototype at the end of this effort.

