**Collaborators:**

## Study Design and Methods

**Methods:** *Describe in lay terms, completely detailing the research activities that will be conducted by Mayo Clinic staff under this protocol.*

Following informed consent Mayo Clinic staff will evaluate the auditory perception of electrical stimulation by comparing the responses to traditional audiological threshold measures and word recognition. Each threshold from 250Hz through 20 KHz will be determined with a method of limits approach for both acoustic and electrostimulation. Once these thresholds are established then we will measure percent correct in standardized word recognition testing using isophonemes and words at a suprathreshold level of 60dB HL.

Of primary interest is the assessment of lateralization of sound within the head by employing 4 channels of electrostimulation to determine the place and degree of separation of sound compared to the traditional lateralization of ear-to-ear with traditional acoustic hearing. These measures will be conducted by changing the level and timing of current between electrode pairs. Given there are four electrode pairs we will establish the critical parameters for timing and current that yield specific patterns of lateralization. Data will be recorded on a spherical plot representing perception within the head.

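### The Data Analysis Plan extrapolates to a safe and highly effective prototype although no safety outcome is described, and the later 60-person trial has two conflicting group splits

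*Protocol*

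**What the plan says.** **The claim.** The Data Analysis section of the protocol gives no power statement because the technology is still in development. Its analysis plan ends by saying that "the resultant data can be extrapolated across other frequencies and input currents to deliver a highly effective and safe prototype".

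**The measurements.** Under Lateralization, and again in the third-phase text, the threshold is found by "increasing the amplitude of the current input until the subject can hear a tone". Study Design and Methods tests word recognition "using isophonemes and words at a suprathreshold level of 60dB HL"; the third phase tests speech "by measuring percent correct in MRT testing at a suprathreshold level". In the first and second phases the participant is to "indicate the lowest level of perception, the location of the signal within the head, and word recognition using a standard work recognition test". The second phase adds one rating: "Participants will be asked to rate the quality of music of the electroacoustic system on a 1-10 scale". The legible endpoints are headsets with two or four channels and the associated algorithms and software.

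**The groups.** The second-phase text recruits 15 participants with bilateral and 15 with asymmetrical hearing impairment, plus 30 with normal hearing. Key Objectives, item 6, plans 20 with bilateral sensorineural loss, 20 with single-sided deafness and 20 with normal hearing. The second-phase localization paragraph calls the one-sided group unilateral.

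**The model.** Masking noise in the second phase "will be presented at suprathreshold levels between 25-50 dB HL at all frequencies", in order to "further develop the modeling from the first phase that will be used to predict electric thresholds using air conduction threshold inputs".

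**The concern.** The extrapolation sentence stands in the analysis plan, so it tells a reader what the data will be able to show. It joins two things that the data would have to carry: a step to currents that were not tested, and a description of the result as safe and highly effective. If nothing that bears on safety is recorded, the word safe has no data behind it, and someone deciding on the next prototype could take it as a study result.

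The group split matters for a different reason. It decides how many hearing-impaired participants there will be, and whether the one-sided group has asymmetrical loss or single-sided deafness. Those labels need not describe the same people.

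A lesser matter is that the threshold model is described as built on normal-hearing listeners, while the aims include hearing-impaired users. Masking in a normal ear may not reproduce real cochlear loss.

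**Working it through.** **1. What each measurement can inform.** The plan gives no figure for this claim, so the check sets the sentence against the measurements in the methods.

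| Measurement (protocol) | Bears on effectiveness? | Bears on safety? |
|---|---|---|
| Perception threshold, all phases | Yes, at the currents used | No |
| Perceived location, all phases | Yes, at the currents used | No |
| Word recognition / rhyme test | Yes, at the level used | No |
| Music rating, 1 to 10, second phase | Yes, at the level used | No |
| Headset endpoints | Development deliverables | No |

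The exclusion criteria restrict who enters, but they measure nothing. For the acoustic masking noise the protocol does argue from level: it sets the 50 dB HL maximum against a loud-sound mark of 85 dB SPL. The legible text has no counterpart for current.

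**2. Frequencies and currents differ.** Thresholds are planned from 250 Hz to 20 kHz, so the frequency range is largely covered by testing. For currents no values are given. They are raised to each participant's threshold, and level and timing are varied between electrode pairs. The tested range will therefore be known only from the data. Extrapolation to other currents is the weak part of the sentence.

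**3. The group split.**

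| Protocol section | Bilateral | One-sided | Hearing-impaired | Normal hearing | Total |
|---|---|---|---|---|---|
| Second phase clinical trial | 15 | 15 (asymmetrical) | 15 + 15 = 30 | 30 | 30 + 30 = 60 |
| Key Objectives, item 6 | 20 (sensorineural) | 20 (single-sided deafness) | 20 + 20 = 40 | 20 | 40 + 20 = 60 |
| Difference | 5 | 5 | 10 | 10 | 0 |

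Subject Information gives 60 for Phase 2, which fits both rows and so cannot decide between them. (That line also states 100 overall, while its parts sum to 30 + 60 + 30 = 120. This is a separate discrepancy and does not settle the split.)

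**4. The model.** The first phase has 30 normal-hearing participants without masking. The second-phase masking work is assigned to 30 normal-hearing participants. The hearing-impaired participants are recruited to evaluate directionality, but the general second-phase procedure has participants report their lowest level of perception, so their thresholds are probably collected. No comparison of predicted with measured electric thresholds in them is described. The documents give no figure from which a bias could be sized.

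**The case against.** **The sentence is an aspiration.** It closes a development plan, and no test, estimand or decision rule depends on it. That is fair and limits the weight of the point. But the sentence is in the analysis plan, and it says what the data can be used to deliver.

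**The missing current range.** A reader might infer that the lack of a preset range is a defect. The documents do not support that: amplitude requirements are among the things Key Objectives sets out to establish, so the range is a result. Nor are the data confined to threshold currents, since level is varied on purpose.

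**Putting a number on the extrapolation.** It is tempting to quote how fast precision falls beyond the data, or what event rate a run without events would rule out. The protocol plans neither a regression on current nor an event count, so such figures would describe a different study.

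**Text that cannot be seen.** Some passages are blacked out, including lines after the endpoints, and a statistical analysis plan may exist. A tolerability outcome could be there. The point is therefore limited to the legible text. Even such an outcome would support safety only at the currents where it was recorded.

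**The group split.** Key Objectives does not call item 6 Phase 2. The match is inferred from the common total of 60, the noise cancellation, and the lateralization or localization work. It is a strong match, but the protocol should say so.

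**The model.** A reader might infer that the hearing-impaired participants serve directionality alone, or are excluded from the model. The protocol says neither. How a model is validated is commonly left to the analysis plan, so this part is optional.

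**Conclusion.** Two points stand.

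First, the measurements in the legible protocol include nothing on safety or tolerability. They cannot support the word safe at any current, and support it least at currents not tested. They can speak to effectiveness, but only within the range tested. This is a limit on what may be concluded. A reader might infer that the device is unsafe, but nothing in the documents says so. The size of any error from extrapolating cannot be derived from the documents.

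Second, the later trial of 60 has two incompatible splits: 30 against 40 hearing-impaired, 30 against 20 normal hearing, and 15 against 20 in each impaired group, with three different names for the one-sided group. This assumes that Key Objectives item 6 and the second phase are the same trial.

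The model check is a suggestion, conditional on thresholds being collected in hearing-impaired participants. The changes to the analysis sentence and the groups should be made; both are cheap.

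**What to change.** 1. **Data Analysis.** Limit the conclusions to the currents and frequencies actually tested and report that range as a result. Remove the description of the prototype as safe and highly effective as a product of extrapolation. If a safety statement is to stay, tie it to a named tolerability outcome recorded at the tested currents. Cost: a wording change and one reported range; a tolerability record is needed only if the safety statement is kept. The price is a narrower claim.
2. **Key Objectives, second-phase text and localization paragraph.** Reconcile group sizes and define the one-sided group once. State whether item 6 is the second phase. Cost: a text correction, unless the chosen split changes recruitment.
3. **Optional.** If electric and air-conduction thresholds are collected in the hearing-impaired participants, compare predicted with measured electric thresholds in them before the model is applied to hearing-impaired users. Cost: a small analysis with no new participants. If those thresholds are not collected, this item falls away.
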